4.2.1 PRIMARY ENDPOINT

Phase Ib:

The primary outcome measurement for Phase IB(SA1) will be defining the Maximal Tolerated Dose(MTD) of topical Verapamil HCl. Dose Limiting Toxicity will be defined as a development of 2nd or 3rd degree heart block as measured by an EKG.

Phase II:

The primary outcome for Phase II(SA2) will be determining the efficacy of topical Verapamil HCl at the MTD for subjective symptoms of CRSwNP using the validated SNOT-22.

4.2.2 SECONDARY ENDPOINTS

Phase Ib:

Intermediate toxicity will be defined as: a heart rate of <50, an asymptomatic BP reduction >30% from baseline or SBP <90mmHg, an asymptomatic AMP reduction >30% from baseline or MAP<55, an asymptomatic DBP reduction >30% from baseline, and a Meltzer Compliance Grade >4.

Mild toxicity will be defined as a Meltzer Compliance Grade of 2-3.

Phase II:

The secondary outcomes of Phase II will be to determine the efficacy of Verapamil HCl at the MTD as measured by a subjective 10cm visual analog scale(VAS), Meltzer topical irrigation satisfaction and compliance scores, and the validated Lund-Kennedy nasal endoscopy score(LKS).

4.2.3 EXPLORATORY ENDPOINTS

Phase Ib:

The efficacy of Verapamil HCl irrigations in the treatment of CRSwNP using validated symptoms outcome test (SNOT-22) and a 10cm visual analogue scale (VAS).

5 STUDY ENROLLMENT AND WITHDRAWAL

5.1 PARTICIPANT INCLUSION CRITERIA

Phase 1 Inclusion:

- Patients presenting to the MEEI Sinus Center
- Age 18-80 yrs old
- Diagnosed with Chronic Rhinosinusitis with Nasal Polyps according to the EPOS 2012 consensus criteria
 Phase 2 Inclusion
- Post-operative with a Lund-Kennedy Poly score of <4
- Baseline SNOT-22 Score ≥ 30
- Patients presenting to the MEEI Sinus Center
- Age 18-80 yrs old
- Diagnosed with Chronic Rhinosinusitis with Nasal Polyps according to the EPOS 2012 consensus criteria

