5.3 STRATEGIES FOR RECRUITMENT AND RETENTION

A concerted effort will be made to recruit male and female subjects equally. Special attention will also be paid to enroll minority subjects into this trial to represent the ethnic demographics of the region as closely as possible. No sex/gender or racial/ethnic group will be excluded from this study.

Patients in the Phase 1B arm will be compensated \$150 per visit at the end of their participation to compensate them for the frequent nature of the visits. Patients in the Phase 2 arm will be compensated \$150 for their participation at the end of their week 4 visit.

All subjects will be recruited from the MEEI Sinus Center. The MEEI Sinus Center has over 3000 outpatient visits per year. This should provide a more than adequate patient pool to recruit from. Patients will be informed of the Phase 1B or Phase 2 trial during a regular clinical visit. If they express interest in the trial the clinical coordinator will explain the parameters of the study and review inclusion/exclusion criteria.

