7.1.2 STANDARD OF CARE STUDY PROCEDURES

Phase 1B: The below procedures are considered routine standard of care in the management of patients with CRSwNP:

- Nasal Endoscopy with scoring
- SNOT-22 and VAS assessment for disease severity

Phase 2: The below procedures are considered routine standard of care in the management of patients with CRSwNP:

- Nasal Endoscopy with scoring
- SNOT-22 and VAS assessment for disease severity
- Clinic examination every 2-4 weeks in patients with CRSwNP

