7.2 LABORATORY PROCEDURES/EVALUATIONS

7.2.1 CLINICAL LABORATORY EVALUATIONS

Screening: A pregnancy test will be done within 24 prior to the first application of topical verapamil in women of child bearing age.

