7.3 STUDY SCHEDULE

7.3.1 SCREENING

Phase 1B:

During the screening visit all exclusion/unclusion criteria will be reviewed. If a participant is a good candidate for the study consent will be obtained. Participants will be given an intake questionnaire which queires the presence of a variety of medical parameters which are relevant to the disease process. A pregnancy test will be administered to any female of child bearing age who is sexually active and not using contraception or admits to a possbility of being pregnant. If the participant has used systemic steroids within the past 3 weeks they will be asked to undergo a 3 week washout of steroids before beginning the trial.

Phase 2:

During the screening visit all exclusion/inclusion criteria will be reviewed. If a participant is a good candidate for the study consent will be obtained. Participants will be given an intake questionnaire which queires the presence of a variety of medical parameters which are relevant to the disease process. A pregnancy test will be administered to any female of child bearing age who is sexually active and not using contraception or admits to a pissbility of being pregnant. If the participant has used systemic steroids within the past 3 weeks they will be asked to undergo a 3 week washout of steroids before beginning the trial.

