7.3.2 ENROLLMENT/BASELINE

Phase 1B:

Participants will fill out the baseline questionnaires (SNOT-22, VAS). An endoscopy will be recorded and scored. A mucus sample will be collected from the nasal cavity with a small sponge. Participants will be instructed in the proper method for using the verapamil irrigation. They will then be given a baseline EKG and asked to perform the first verapamil irrigation while being monitored for 1 hour by clinical monitoring equipment and study staff. After monitoring the patients will be given a second EKG. The irrigant will be collected. If no EKG abnormalities that are deemed unsafe by the study safety officer are detected during or after the initial irrigation the participants will be prescribed the rest of the verapamil rinse.

Phase 2:

Participants will fill out the baseline questionnaires (SNOT-22, VAS). An endoscopy will be recorded and scored. A mucus sample will be collected from the nasal cavity with a small sponge. Participants will be instructed in the proper method for using the verapamil irrigation. They will then be given a baseline EKG and asked to perform the

first verapamil irrigation while being monitored for 1 hour by clinical monitoring equipment and study staff. After monitoring the patients will be given a second EKG. The irrigant will be collected. If no EKG abnormalities that are deemed unsafe by the study safety officer are detected during or after the initial irrigation the participants will be prescribed the rest of the verapamil rinse.

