7.3.7 SCHEDULE OF EVENTS TABLE

4	Phase Ib			Phase II			
Procedures	Screening	Enrollment/ Baseline	Weekly/Final Follow-up	Screening	Enrollment/ Baseline	Follow-up (Day 7)	Final Visit (Day 28)
Informed Consent (IC)	X		-	х			
Intake Form (IF)	X	3	į	x		3	
Pregnancy Test (PT)	X			x			
SNOT-22	100	х	х		х	х	X
Visual Analog Scale (VAS)	3	х	x		х	х	X
Electrocardiogram (EKG)		х	х		x	x	
Heart Rate (HR)		х	х		х	х	X
Blood Pressure (BP)	ŝ.	x	x		x	x	х
Lund-Kennedy Score (LKS)		x	x		х	x	X
Nasal irrigation (NI)		х	х		х		х
Mucus sponge (MS)	ý.	x	х		x	- 3	х
Satisfaction Scale (SS)		d	x			Х	х
Compliance Scale (CS)			×			×	х
Side effects (SE)			x			х	X

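### As scheduled, one SNOT-22 score both admits Phase II patients (30 or more) and starts the uncontrolled change score, so part of any fall can be regression to the mean

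*Combined protocol and SAP*

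**What the plan says.** Section 5.1 lists "Baseline SNOT-22 Score ≥ 30" among the Phase 2 inclusion criteria. Section 7.3.1 says of Phase 2: "During the screening visit all exclusion/inclusion criteria will be reviewed". The screening tasks it goes on to describe are consent, the intake questionnaire, a pregnancy test and, where needed, steroid washout. No SNOT-22 is among them.

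The first SNOT-22 appears in section 7.3.2: "Participants will fill out the baseline questionnaires (SNOT-22, VAS". The schedule of events (7.3.7) agrees. For Phase II it marks SNOT-22 at Enrollment/Baseline, Day 7 and Day 28, and leaves the Screening cell blank.

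The primary null hypothesis (10.2) is no mean difference between baseline and 4-week SNOT-22. Section 10.4.2 tests differences from baseline. All 20 Phase II patients receive verapamil (4.1), and section 10.6.1 rules out blinding and randomization.

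Two passages point to a possible earlier score. Section 5.3 says "Patients will be informed of the Phase 1B or Phase 2 trial during a regular clinical visit", and section 7.1.2 lists "SNOT-22 and VAS assessment for disease severity" as routine care. Neither says that such a score decides eligibility.

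**The concern.** A single SNOT-22 score contains a stable part and a part that varies from one occasion to the next. Requiring 30 or more on one occasion favours patients whose varying part happened to be high that day. If that same reading is the baseline, the mean at the next reading is expected to be lower without any treatment effect. A concurrent control group would show the same fall and cancel it; this design has none.

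The primary test is against zero, not against the MCID, so even a modest built-in fall raises the chance of declaring an improvement that is not there. The baseline-adjusted regression models in 10.1 do not help, because in a single arm they do not take the selection effect out of the mean change.

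**Working it through.** **Inputs from the plan (10.1, 10.5).** SD of a single score 30; r² between time points 50%, so ρ = √0.5 = 0.7071; SD of change 24; target 15.9; n = 20; significance level 0.05; power 80%; MCID 8.9. The SD and r² come from the oral verapamil trial over 8 weeks.

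**Assumptions not in the plan.** The mean SNOT-22 of unselected clinic patients, m, is taken as 40, 50, 60 and 70. These patients have the SD and ρ above. Scores are roughly normal, and are limited to 0–110 in the simulation.

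**The plan's own figure.** A paired t-test, two-sided 0.05, with effect 15.9 and SD 24 has power 0.802 at n = 20, so the stated sample size reproduces. A one-sided test would need only 16, so I take the test as two-sided, with 2.5% on the improvement side.

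**Expected fall with no drug effect.** With a = (30 − m)/30, and φ and Φ the standard normal density and distribution function:

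fall = (1 − ρ) × 30 × φ(a) / (1 − Φ(a))

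At m = 40: a = −0.333, φ(a) = 0.3774, 1 − Φ(a) = 0.6306, ratio 0.5985, so fall = 0.2929 × 30 × 0.5985 = 5.26.

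The remaining rows come from the same formula and from simulated trials of 20 patients, selected on baseline ≥ 30, with both scores limited to 0–110 and a paired t-test (critical t 2.093).

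| Assumed mean m | 40 | 50 | 60 | 70 |
|---|---|---|---|---|
| Fall, formula | 5.26 | 3.76 | 2.53 | 1.59 |
| Fall, scores limited to 0–110 | 5.13 | 3.69 | 2.51 | 1.57 |
| False significant improvement | 17% | 11% | 7% | 5% |
| Share of the smallest significant fall | 46% | 33% | 22% | 14% |

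The last row uses the plan's SD of change: the smallest significant mean fall is 2.093 × 24 / √20 = 11.23, and 5.13 / 11.23 = 0.46, and so on. The simulated SD of change is about 21 to 22, so these shares are slightly low if anything.

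**Sensitivity (m = 40, 50, 60, 70).**
- SD 20, ρ 0.7071, formula: 2.98, 1.68, 0.81, 0.32 points.
- SD 30, ρ 0.80, formula: 3.59, 2.56, 1.73, 1.08 points.
- SD 20 and ρ 0.80 together, limited scores: about 2.0, 1.1, 0.5 and 0.2 points; false improvement about 10%, 6%, 4% and 3%.
- In the other direction, a mean of 30 with the plan's SD and ρ gives 7.0 points by formula. A correlation of 0.50 at mean 40 gives 9.0.

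**Effect of a separate qualifying score.** The remaining fall depends on how much more strongly the qualifying score correlates with baseline (r) than with week 4. If the correlation with week 4 is 0.7071, the share of bias left is (r − 0.7071) / (1 − 0.7071).

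| r, qualifying score with baseline | 0.7071 | 0.80 | 0.90 | 0.95 |
|---|---|---|---|---|
| Share of bias left | 0% | 32% | 66% | 83% |
| Fall at m = 40 | 0.0 | 1.6 | 3.4 | 4.2 |
| False improvement at m = 40 | 2.5% | 5% | 9% | 13% |

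**The case against.** The strongest reply is that the one-score reading is an inference. Section 7.3.1 reviews all criteria at screening and seeks consent from good candidates. A threshold of 30 cannot be reviewed then unless a score already exists, and SNOT-22 is routine care. On that reading a clinic score qualifies the patient and the baseline score is new. The schedule is also not a complete list of screening items: the screening EKG implied by section 5.2 is not in it. This stands as a possibility. But section 5.1 names the baseline score, and nothing in the text available to me (the design schematic is not shown) gives an earlier score that role. At the least, the plan does not say which score qualifies.

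A second reply is that the size is uncertain. The clinic mean is not given, and the SD and r² come from another drug route over 8 weeks. If that r² includes treated patients, it may understate the untreated 4-week correlation. This also stands: the percentages are illustrations, and the least favourable headline figure depends on an assumed mean of 40. Smaller SD and higher correlation shrink the effect but do not change its direction.

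A third reply is that an open-label single-arm cohort cannot support a causal claim anyway. That is true of placebo response and natural change. The selection component differs in that it can be reduced without adding a control group.

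**Conclusion.** The concern holds. As the plan is scheduled, the same SNOT-22 reading selects Phase II patients and starts the primary change score, with no comparison group to remove the resulting fall. With the plan's SD and r², and assumed clinic means of 40 to 70, the built-in fall is 5.1 down to 1.6 points, and the improvement-side error rate is about 17% down to 5% instead of 2.5%. If the SD is 20 and the correlation 0.80, the range is about 2.0 down to 0.2 points and 10% down to 3%. In both cases the artefact is below the 8.9-point MCID and well short of 15.9, so it would inflate a result rather than create the target effect. The direction is firm under the scheduled reading; the size is not, because the screened population's mean and 4-week correlation are not in the documents. The plan should be changed, but this does not undermine the sample size, which stays at 20.

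**What to change.** - Apply the threshold of 30 to a SNOT-22 from an earlier, separate occasion: the screening visit, or a documented prior clinic visit. Say so in 5.1, 7.3.1 and 7.3.7.
- Keep the Enrollment/Baseline SNOT-22 as the analysis baseline whatever its value.
- State a minimum interval between the two scores. None is given in the text available. Screening can precede baseline by weeks for patients on recent steroids ("they will be asked to undergo a 3 week washout of steroids before beginning the trial"). Yet the schedule puts the pregnancy test at screening while section 7.2.1 says "A pregnancy test will be done within 24 prior to the first application of topical verapamil in women of child bearing age", with the unit missing, so for some patients the two visits may be very close. For them a prior clinic score is the better qualifying score, since two readings close in time leave much of the bias in place.
- Record as a limitation that placebo response and natural change remain.

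The cost is one extra questionnaire, or use of a score already taken in routine care. The observed effect may be smaller. Some patients will have a baseline below 30: with equal correlations, about 19%, 13%, 9% and 5% at assumed means of 40, 50, 60 and 70 (3.7, 2.6, 1.8 and 1.1 of 20). Section 5.1 must therefore no longer describe the threshold as applying to the baseline score.

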5.2 PARTICIPANT EXCLUSION CRITERIA

Patients with the following comorbidities:

- •GI Hypomotility
- •Heart Failure
- •Liver Failure
- Kidney Disease

 Muscular Dystrophy Pregnant or Nursing Females •Systemic Steroid Dependency Hypertrophic Cardiomyopathy •Any Atrial or Ventricular arrhythmia (ie. Atrial fibrillation, atrial flutter, etc..) •Resting Heart Rate less than 60 beats per minute •Baseline Systolic Blood Pressure less than 110 mmHg •Baseline Diastolic Blood Pressure less than 70 mmHg •Baseline Mean Arterial Pressure Less than 60 mmHg •PR interval less than 0.12 seconds Patients taking the following medications: Aspirin Beta-blockers Cimetidine(Tagamet) Clarithromycin(Biaxin) Cyclosporin Digoxin Disopyramide(Norpace) Diuretics Erythromycin Flecainide •HIV Protease Inhibitors(Indinavir, Nelfinavir, Ritonavir) Quinidine •Lithium Pioglitazone

Rifampin

•St Johns Wort

Patients who are unwilling or unable to wash out of systemic steroids

Patients with cardiac or conduction abnormality picked up by screening EKG

Post-op patients with surgery within 3 months prior to enrollment.

5.3 STRATEGIES FOR RECRUITMENT AND RETENTION

A concerted effort will be made to recruit male and female subjects equally. Special attention will also be paid to enroll minority subjects into this trial to represent the ethnic demographics of the region as closely as possible. No sex/gender or racial/ethnic group will be excluded from this study.

Patients in the Phase 1B arm will be compensated \$150 per visit at the end of their participation to compensate them for the frequent nature of the visits. Patients in the Phase 2 arm will be compensated \$150 for their participation at the end of their week 4 visit.

All subjects will be recruited from the MEEI Sinus Center. The MEEI Sinus Center has over 3000 outpatient visits per year. This should provide a more than adequate patient pool to recruit from. Patients will be informed of the Phase 1B or Phase 2 trial during a regular clinical visit. If they express interest in the trial the clinical coordinator will explain the parameters of the study and review inclusion/exclusion criteria.

5.4 PARTICIPANT WITHDRAWAL OR TERMINATION

5.4.1 REASONS FOR WITHDRAWAL OR TERMINATION

Arm 1: Phase 1B

The PI will terminate a Phase IB participant if they experience a DLT, more than one IT, or begin a contradictory medication during the course of the trial. Patients may withdraw from the trial at any time upon request. Any withdrawn participants from Phase IB will be replaced to maintain 3 patient cohorts. Their reason for withdrawal will be noted.

Arm 2: Phase 2

The PI will terminate a Phase II study participant if they present with any clinical adverse event (AE) or other medical complication such that continued participation in the study would not be in the best interest of the participant. The PI will terminate a participant if they miss more than 2 doses of topical Verapamil in a week. Compliance will be checked using a patient dosing diary. Participants may withdraw from the trial at any time upon request. Any withdrawn participant will be replaced with a new enrollment.

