2.3 POTENTIAL RISKS AND BENEFITS

2.3.1 KNOWN POTENTIAL RISKS

Verapamil HCl is a cardioactive drug and thus there is a theoretical risk of cardiac side effects from the medication. This will be mitigated by obtaining a EKG which will be reviewed by a medical internist/anesthesiologist prior to initiating therapy. Follow-up EKGs will also be performed to monitor for cardiac side effects. The risk of cardiac effects appears to be dose-dependant and is expected to be mostly reversible upon discontinuation of the drug. Additional risks include bradycardia and hypotension. These will be mitigated by checking routine vital signs at each visit which will include heart rate and blood pressure. Constipation is also a risk of the drug. This will be asked about at each visit and stool softeners and/or laxatives will be administered as necessary. Since verapamil will be administered with a nasal rinse there is a possibility of nasal irritation. These side effects will be monitored at each study visit.

There are currently few medical interventions available for CRSwNP. The development of new medications is critical to the management of this disease. Thus, the short-term risks for the trial patients will ultimately decrease the risks and discomforts that the overall CRSwNP population experiences.

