4 STUDY DESIGN AND ENDPOINTS

4.1 DESCRIPTION OF THE STUDY DESIGN

ARM 1: Phase 1B

The phase IB study will consist of an accelerated titration, intrapatient dose escalation cohort, with double-dose step design. The initial single patient cohort will begin by taking 0.3mg (10mg of Verapamil in 240mL of buffered normal saline yielding an established 3% residual nasal dose) as a nasal irrigation BID for 1 week. The first dose f

each escalation will be administered in a 10th or 11th floor MEE clinic withhemodynamic monitoring. A medically trained member of the study staff with monitor the patient for one hour. Patients will be instructed on the how to properly perform the irrigation using a pre-recorded video demonstration. If no first-course dose limiting toxicity (DLT, defined by the development of 2nd or 3rd degree heart block) is noted then patients will continue taking the current Verapamil rinse dose BID for 1 week. Dose escalation will occur weekly in the absence of a single, any course, DLT or a second, any course, intermediate toxicity(IT, defined by a heart rate of <50, an asymptomatic BP reduction >30% from baseline or systolic BP <90mmHg, an asymptomatic MAP reduction >30% from baseline or MAP<55, an asymptomatic diastolic BP reduction >30% from baseline, and a Meltzer Compliance Grade >4[60]). Each escalation will be a doubling of the dose from 0.3-2.4mg. At that point that dose will escalate in 0.6mg residual intervals for the rest of the trial up to a maximum of 3.6mg total residual dose. These doses were derived from the pharmacokinetic analysis of our oral Verapamil trial results. If a single, any course, DLT or second, any course, IT occurs, two additional patients will be recruited at that identified dose and Phase IB will revert to a standard 3+3 design. If any patient un-enrolls while the dose escalation is still occurring, they will be replaced to maintain 3 patient cohorts. The maximal administered dose(MAD) will be considered that at which at least 2 DLTs or 4 ITs occur and the MTD will then be assigned to the immediate preceeding dose.

At each weekly visit, the patients nasal endoscopy will be recorded for LKS grading, and they will be administered symptom, side-effect, and tolerability questionnaires. Pre-dosing mucus and post-dosing irrigant samples will also be atraumatically collected from the nasal cavity for use in exosomal biomarker sampling.

ARM 2: Phase 2

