The Phase II study will be an open label safety and efficacy expansion cohort using the MTD determined in the Phase IB arm. A total of 20 patients will be administered the MTD of topical Verapamil HCl in a 240mL buffered normal nasal rinse for 4 weeks BID. This sample size was calculated based on a power analysis derived from the results of our oral Verapamil trial. The first dose will be administered in in a 10th or 11th floor MEE clinic withhemodynamic monitoring. A medically trained member of the study staff with monitor the patient for one hour. Patients will be instructed on the how to properly perform the irrigation using a pre-recorded video demonstration. If no first-course DLT occurs then patients will continue taking the topical Verapamil dose BID. Patients will then return for follow-up visits at 1 week and 4 weeks. Subjective and objective outcome measures will be collected at each visit.

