7.3.3 FOLLOW-UP

Phase 1B:

Participants will asked to fill out a SNOT-22, VAS, , Satisfaction scale, and Compliance scale. Adherence to the treatment regimen will be evaluated. An endoscopy will be recorded and scored. A mucus sample will be collected from the nasal cavity with a small sponge. Participants will be evaluated for side-effects. An EKG will be taken. If no intermediate toxicity or DLT is experienced the participant will be moved up to the next dose. Participants will be asked to perform the initial irrigation of their next dose while being monitored for 1 hour by clinical monitoring equipment. After monitoring the patients will be given a second EKG. The irrigant will be collected. If no EKG abnormalities that are deemed unsafe by the study safety officer are detected during or after the initial irrigation the participants will be prescribed the rest of the verapamil rinse.

Phase 2:

During the Week 1 follow-up visit participants will asked to fill out a SNOT-22, VAS, , Satisscation scale, and Compliance scale. Adherence to the treatment regimen will be evaluated. Participants will be evaluated for side-effects. An EKG will be taken. An endoscopy will be recorded and scored.

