7.3.4 FINAL STUDY VISIT

Phase 1B:

Participants will have their final study visit when they experience DLT and are removed from the study, choose to end their participation, or achive the maximal administered dose. The reason for the drop-out will be noted in the participant file. Participants will be asked to fil out a SNOT-22, VAS, Satisfaction scale, and Compliance scale and will be evaluated for side-effects. An endoscopy will be recorded and scored. A mucus sample will be collected from the nasal cavity with a small sponge. Participants will receive their compensation at the end of the final visit.

Phase 2:

During the Week 4 visit participants will be asked to fill out a SNOT-22, VAS, Satisfaction scale, and Compliance scale. Adherence to the treatment regimen will be evaluated. Participants will be evaluated for side-effects. An endoscopy will be recorded and scored. A mucus sample will be collected from the nasal cavity with a small sponge. Participants will receive their compensation at the end of the final visit.

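### In Phase II, heart block found after the monitored first irrigation is not named as an automatic reason to stop verapamil, although it is in Phase Ib

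*Combined protocol and SAP*

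**What the plan says.** Sections 4.1 and 4.2.1 define the DLT as 2nd or 3rd degree heart block on EKG.

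**Phase Ib.** Section 5.4.1 makes it a mandatory stop: "The PI will terminate a Phase IB participant if they experience a DLT, more than one IT, or begin a contradictory medication". Section 7.3.4 repeats this: "Participants will have their final study visit when they experience DLT and are removed from the study". Section 7.3.3 allows the next dose only when neither an intermediate toxicity nor a DLT has occurred.

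**Phase II.** Under section 5.4.1 the PI is to "terminate a Phase II study participant if they present with any clinical adverse event (AE) or other medical complication such that continued participation" would be against the participant's best interest. Section 4.1, directly after describing the hour of monitoring at the first dose, says: "If no first-course DLT occurs then patients will continue taking the topical Verapamil dose BID". Section 7.3.2 makes the remaining supply depend on the safety officer's view of EKGs around the initial irrigation. For Week 1, section 7.3.3 says "An EKG will be taken. An endoscopy will be recorded and scored" and links no decision to the tracing. Section 10.4.7.1 names who assesses that EKG, but not what follows from it. The schedule in 7.3.7 marks Phase II EKGs at baseline and Day 7 only.

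**Management of heart block.** Section 8.1 adjusts treatment to symptoms. A patient with no symptoms may be observed; symptomatic patients move up through fluids, calcium, other drugs and pacing. It does not say whether verapamil is stopped.

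**The concern.** The event that the trial itself calls dose limiting ends dosing in Phase Ib without discretion. In Phase II, once the first irrigation has passed, the same event is left to a general clause that does not mention it. The same Phase II paragraph does contain a fixed rule for adherence: missing more than two doses in a week means termination. So the plan has an automatic stop for missed doses but none for its own cardiac endpoint.

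What is at stake is the individual participant. Section 2.3.1 says: "The risk of cardiac effects appears to be dose-dependant and is expected to be mostly reversible upon discontinuation of the drug". Withdrawing the drug is therefore the remedy that the protocol itself relies on. The Phase II dose need not be free of heart block either. Under section 4.1 the maximal administered dose "will be considered that at which at least 2 DLTs or 4 ITs occur", and the MTD is the dose just below it, so the MTD can already have produced one DLT.

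**Working it through.** This is mainly a comparison of texts. The plan states no figure on this point to reproduce.

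**Step 1. Automatic stop for a DLT, by phase.**

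| Place | Phase Ib | Phase II |
|---|---|---|
| 5.4.1 | DLT named, termination mandatory | DLT not named; best-interest clause |
| 7.3.4 | Removal on DLT | No counterpart |
| 7.3.3 | Next dose only without DLT or intermediate toxicity | EKG taken; no action stated |
| 4.1 | First-course check, then any-course rule for escalation | First-course check only |
| 7.3.2 | EKG check around initial irrigation | Same check, same limit |

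**Step 2. Does the check in 4.1 reach beyond the first irrigation?** The Phase Ib text of 4.1 uses a separate term for later events: "Dose escalation will occur weekly in the absence of a single, any course, DLT". The Phase II text uses only the first-course term and places it right after the monitored first dose. Section 7.3.2 also limits its check to the initial irrigation. The more natural reading is that the check covers the first irrigation only.

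**Step 3. Do the study-level halts stand in for an individual stop?** Section 10.4.7.1 halts Phase II at 20% with a severe adverse event, at the DSMB's discretion. With 20 participants:

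- threshold: 0.20 × 20 = 4 participants
- one DLT: 1/20 = 5%

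Section 8.5 halts the trial at a 20% adverse event rate and gives no denominator. One event among the first five participants (1/5 = 20%) could trigger it, but later in enrolment one event would not. Both rules act on the arm or the trial and not on the person with the block.

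**Step 4. Is a reduced dose a middle course?** No. Section 6.1.8 keeps the Phase II dose fixed for the four weeks, so the choice is to continue or to stop.

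**Step 5. How much dosing is exposed?** Inputs: twice daily for 4 weeks (4.1), last scheduled EKG at Day 7 (7.3.7).

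- total irrigations: 28 × 2 = 56
- given by Day 7: 7 × 2 = 14
- remaining: 21 × 2 = 42
- share remaining: 42/56 = 75%

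If a block is seen at Day 7 and dosing continues, up to 42 irrigations follow with no scheduled EKG. The early termination visit (7.3.5) copies the final visit, so it adds none. Heart rate and blood pressure are measured at Day 28.

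**The case against.** **The best-interest clause is mandatory in form.** It says that the PI will terminate, not that the PI may. New 2nd or 3rd degree block on a cardioactive drug, in people screened for conduction abnormality (5.2), is a plain case for it. This stands. A reader might infer that nothing in Phase II requires verapamil to be stopped; the documents do not support that. What is missing is DLT as a named, automatic trigger.

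**Section 8.1 can be read as acute care only.** Observation is the lowest rung of a rescue ladder, and the section also serves Phase Ib, where every DLT ends participation. Observation and a stop can therefore coexist. This also stands: a reader might take 8.1 as permission to keep dosing, but it does not say so. It is silent on the drug, and in Phase II no other sentence fills that silence.

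**First-course is undefined.** Phase II has one course, and 6.1.8 speaks of a four-week course. On that reading, 4.1 would already cover all four weeks. Placement and 7.3.2 favour the narrower reading but do not settle it, so confidence is moderate.

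**Other safeguards exist.** Adverse events go to the IRB and DSMB (8.4.1) and are followed to resolution (8.3). A high-grade block could meet the serious-event definition (8.1.2). An internist/anesthesiologist who chairs the DSMB reviews all EKGs (section 9). Participants terminated for an adverse event are followed for up to a year (5.4.2). These detect, report and follow the event; none of them requires the drug to be stopped.

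**The event may be rare.** The 3.6 mg cap is 3.6/72.75 = 4.9% to 3.6/16.8 = 21.4% of the stated oral-equivalent twice-daily dose (2.1). That is fair. The documents give no block rate, so any probability of a case among 20 participants would rest on an assumed rate. It would also not measure the chance that a detected block is kept on drug.

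**Conclusion.** The point holds as a gap in the Phase II stopping rules and should be corrected. A DLT found after the monitored first irrigation is an automatic stop in Phase Ib and a matter of judgment in Phase II. The PI would probably stop the drug, but the plan as written allows continued dosing in a participant with asymptomatic block.

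Its size is a worst case: up to 42 of 56 irrigations (75%) after a block seen at Day 7. That assumes detection at Day 7, no symptoms, and a decision to continue after EKG review. It is not an estimate of how often this would happen. Confidence is moderate, because it depends on reading the first-course check as limited to the first irrigation and on the silence of 8.1.

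**What to change.** Add to the Phase 2 part of 5.4.1: *Verapamil will be stopped in any participant with a DLT at any visit, with or without symptoms, and the EKG repeated until the block resolves.* In 8.1, state that observation of an asymptomatic patient describes acute management after verapamil has been stopped.

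The cost is one sentence and one clarification, with no added procedures for unaffected participants. An affected participant needs unscheduled EKGs and loses on-treatment Week 4 data, although 7.3.5 already asks for the final-visit procedures. That participant is also replaced under 5.4.1, which means one more enrolment per case. The rule acts only on a block that is detected. It does not supply an EKG after Day 7 for participants whose EKGs up to Day 7 showed no block; that is a separate scheduling question.
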